We will perform sparse sampling pre-dose and at 1, 2.5, 4, 6 and 8 hours after TB drug dosing at day 3 of TB treatment and store plasma at -80°C. Isoniazid, rifampicin and pyrazinamide concentrations will be measured using LC-MS. The PK measurements will be performed on stored, batched samples and thus results of these assays will not be available in real-time and thus will not influence patients management. The UCT Clinical Pharmacology Laboratory has performed many TB drug PK studies [69, 73-75]. Population PK modelling will be used to predict important PK parameters (C_{max} and AUC). Findings would inform further research to optimize initial dosing or route of administration (eg. intravenous) of TB medication in severe HIV-TB.

Methodology:

Study design:

Prospective cohort study of 660 HIV-TB inpatients.

Sample size calculations:

The primary outcome was dichotomised (survivors vs fatal outcome). The calculations have been performed for major experiments relating to urinary LAM concentration, plasma LPS concentration and proportion with detectable CMV viraemia. Cumulative mortality of 15% has been factored: lower than reported (9). We assume in a prospective study with ART initiation at 2-8 weeks mortality will be lower than reported from routine settings.

Urinary LAM concentration (ng/ml). Mean level of urinary LAM of 1.62 ng/ml in survivors has been estimated based on HIV-TB outpatient data obtained from author of [76], [name]:

Survivors Urinary LAM (Mean; SD)	Fatal outcome Urinary LAM (Mean; SD)	Fold change	Alpha	Beta	Sample size
1.62; 3.2	2.43; 3.2	1.5	0.05	0.2	962
1.62; 3.2	3.24; 3.2	2	0.05	0.2	242
1.62; 3.2	4.05; 3.2	2.5	0.05	0.2	108

Plasma LPS concentration (pg/ml). Mean level of LPS in survivors of 128 pg/ml estimated, based on [17]:

Survivors Plasma LPS (Mean; SD)	Fatal outcome Plasma LPS (Mean; SD)	Difference %	Alpha	Beta	Sample size
128, 56	160, 56	25	0.05	0.2	160
128, 56	154, 56	20	0.05	0.2	286
128, 56	147, 56	15	0.05	0.2	536

Detectable CMV viral load by PCR (> 150 copies/ml). Based on [48] it was estimated that CMV viraemia would be detectable in 10-20% survivors (higher than in [48] because participants will have more advanced HIV):

Survivors % CMV viral load detectable	Fatal outcome % CMV viral load detectable	Alpha	Beta	Sample size
20%	40%	0.05	0.2	334
20%	30%	0.05	0.2	1178
10%	30%	0.05	0.2	246
10%	20%	0.05	0.2	786

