660 patients will be enrolled. Assuming 5% loss to follow up, 630 patients will complete the study. We will exclude from major analyses patients diagnosed with rifampicin resistance (estimated 5% [77], n=30), leaving 600 for analysis. This will allow us to detect statistical significance for a two-fold difference in urinary LAM, a 15% difference in plasma LPS and a difference in the percentage of patients with detectable CMV viraemia of 20% in survivors and 40% in those with fatal outcome (or 10% and 30% respectively).

Sample size for FACS experiments (44 fatal cases vs 246 survivors) was based on Annexin-V experiments, allowing us to detect a significant difference in the proportion of CD4 T-lymphocytes that are Annexin-V+ of 5% in survivors and 20% in those who die (alpha=0.05, beta=0.2).

Characteristics of the study population:

Number of participants:

660 participants with HIV-TB co-infection.

Inclusion criteria:

1. Microbiological diagnosis of TB, or clinical diagnosis that fulfills WHO criteria for smear-negative or extrapulmonary TB [78] or suspected to have active TB based on clinical presentation
2. 18 years or older
3. Informed consent from patient (unless drowsy/confused – see below)
4. HIV seropositive
5. CD4 count \leq 350cells/ μ l

Exclusion criteria:

1. HIV seronegative or testing declined
2. Pregnant
3. 3 or more doses of TB treatment received during the admission or has been on TB treatment within one month of admission

TB case definitions:

TB will be investigated with 2 sputa for Xpert MTB/RIF and TB culture, Myco/F Lytic blood culture, urinary lipoarabinomannan (LAM) and samples from appropriate extrapulmonary sites for TB culture. Chest radiographs will be performed in all and abdominal ultrasound at clinician discretion. We will stratify analyses according to:

- 1) Confirmed TB: Microbiologically proven TB (by culture or Xpert MTB/RIF, or post-mortem findings of AFB+ or culture+) (predicted to be > 70% based on previous study at our hospital [79])
- 2) Probable TB: TB not confirmed, but urinary LAM+ or fulfill WHO criteria [78] unless an alternate diagnosis is made during follow-up or post-mortem.

Vulnerability:

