Data quality control and assurance measures will be put in place. These will include having all clinical data capture forms being checked and signed off by one other member of the study team. Data entered on the study database will be entered by one data capturer, but will be checked by a member of the study team or by another data capturer. Any errors will be recorded and discussed at the monthly study meeting. Upon completion of the study we will ensure that 3 copies of the raw data are backed-up for long term storage: one on a UCT server, one on a remote server and one on an external hard-drive that the applicant will keep secure. These data capture, entry, management and access systems have been developed in the course of many TB-HIV and other HIV studies that we have undertaken to date.

Data analysis:

TB suspects who do not have active TB (after full clinical investigation has been completed and all results obtained) will not be included in the analysis of primary endpoints. Their data may be used in secondary analyses or as control subjects. Univariate analysis will compare those who survive 12 weeks to those with fatal outcome. Bonferroni correction for multiple comparisons will be performed where appropriate. Multivariable logistic regression modeling will be approached based on pre-specified hypotheses, articulated where possible through directed acyclic graphs. Demographic variables, CD4 count, viral load, antibiotic treatment will be explored as potential confounders in addition to hypothesis specific variables. Comparison with non-TB control patients will be performed for several of the experiments as described. Data will be analyzed using de-identified study numbers.

Description of risks and benefits:

Potential risks and discomforts: This is an observational trial and there are no study specific interventions. Collection of study samples by means of phlebotomy carries minimal risk of bruising, infection at the collection site and bleeding after phlebotomy. Phlebotomy may be uncomfortable or painful during the procedure, but this resolves as soon as the procedure has been completed. The total volume of blood drawn is ~ 55ml. This amount of blood drawn would not cause complications unless patients are severely anaemic.

Risk classification: The study as a whole carries minimal risk for participants and harm due to study participation is not anticipated.

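### The protocol names single-step Bonferroni where Holm's step-down procedure gives the same error control with never less, and usually more, power for each comparison

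*Protocol*

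**What the plan says.** The Data analysis section plans univariate comparisons of 12-week survivors with fatal cases and then states: "Bonferroni correction for multiple comparisons will be performed where appropriate". It does not say which comparisons form a family, how many there are, or what adjusted level applies.

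The Sample size calculations section sizes three exposures: "The calculations have been performed for major experiments relating to urinary LAM concentration, plasma LPS concentration and proportion with detectable CMV viraemia". Each table row uses alpha 0.05 and beta 0.2 with no adjustment, and the split between groups follows from this assumption: "Cumulative mortality of 15% has been factored". The rows that matter here are:

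- LPS, 15% difference: "128, 56 147, 56 15 0.05 0.2 536"
- LAM, two-fold difference: "1.62; 3.2 3.24; 3.2 2 0.05 0.2 242"
- CMV viraemia: "20% 40% 0.05 0.2 334"

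After loss to follow-up and exclusion of rifampicin resistance, 600 patients remain for analysis. The protocol concludes: "This will allow us to detect statistical significance for a two-fold difference in urinary LAM, a 15% difference in plasma LPS", together with CMV viraemia of 20% against 40% (or 10% against 30%).

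**The concern.** Single-step Bonferroni tests each of m comparisons at alpha/m, however many of the others have already been rejected. Holm orders the p-values and tests the smallest at alpha/m, the next at alpha/(m-1), and so on, stopping at the first failure. Both hold the family-wise error at alpha or below without any assumption about dependence, so for hypothesis tests Bonferroni gives up power and gains nothing in error control.

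The first aim is to find which of several factors are associated with mortality. Power for each factor is therefore what counts, and that is where the two procedures differ. The sizing leaves limited slack for LPS: 536 patients needed at an unadjusted 0.05, with 600 planned.

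**Working it through.** **Inputs (protocol).** 600 analysed, 15% mortality: 90 deaths, 510 survivors. LPS 128 v 147 pg/ml, SD 56 (difference 19). LAM 1.62 v 3.24 ng/ml, SD 3.2. CMV 20% v 40%.

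**Assumptions.** Two-sided tests (sidedness is not stated); a family made up of these three exposures.

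**1. Reproduce the protocol's LPS figure.** Survivors needed = (z₁₋α/₂ + z₁₋β)² × SD² × (1 + 85/15) / difference².

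At alpha 0.05 and 80% power: 7.849 × 3136 × 6.667 / 361 = 454.6, so 455 survivors. Deaths: 455 × 15/85 = 80.3, so 81. Total 536, as stated. The same formula gives 242 for two-fold LAM. The CMV figure of 334 is reproduced with a continuity-corrected two-proportion formula at the same split. The two-sided reading and the 15:85 split therefore match the protocol's own method.

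**2. LPS power at 510 v 90.** Standard error = 56 × √(1/510 + 1/90) = 56 × 0.1143 = 6.403. Expected z = 19 / 6.403 = 2.968.

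- alpha 0.05: Φ(2.968 − 1.960) = 84.3%
- alpha 0.05/2: Φ(2.968 − 2.241) = 76.6%
- alpha 0.05/3: Φ(2.968 − 2.394) = 71.7%

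Bonferroni with m = 3 always uses the last level. For 80% power at that level: 10.469 × 3136 × 6.667 / 361 = 606.3, so 607 survivors and about 107 deaths, roughly 714 analysed patients against 600 planned.

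**3. The other two exposures.** LAM: 1.62 / (3.2 × 0.1143) = 4.43. CMV: 0.20 / √(0.2×0.8/510 + 0.4×0.6/90) = 0.20 / 0.0546 = 3.66, or about 3.95 if matched to the power of a test with pooled variance. Both values were used.

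**4. Holm.** LPS is tested at 0.05/3, 0.05/2 or 0.05, depending on how many of the other two are rejected ahead of it. Its power therefore lies between the 71.7% and 84.3% of step 2, and where it falls depends on whether the other effects are real. One million simulated triples of normal test statistics, with correlations 0, 0.3 and 0.5, give these LPS powers:

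| True LAM and CMV effects | Bonferroni | Holm |
|---|---|---|
| LAM two-fold, CMV 20% v 40% | 72% | 83-84% |
| LAM two-fold, CMV null | 72% | 77% |
| LAM 1.5-fold, CMV 20% v 30% | 72% | 74-77% |
| Both null | 72% | 72% |

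**5. Other measures.** With all three effects as sized and independent tests, the chance of detecting all three under Bonferroni is 0.717 × 0.979 × 0.898 = 63%, against 80% under Holm by simulation (66% v 82% with the larger CMV value). The chance of at least one rejection is the same under both procedures in every scenario.

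**The case against.** The strongest objection is that this is a choice between two valid methods. Bonferroni controls the error as promised, nothing in the Data analysis section is false, and the correction is qualified by a clause leaving its scope to judgement. That stands in part: there is no error of validity. But the protocol does fix a named method, and another method rejects everything it rejects at the same error level, so the change is more than taste.

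Second, the family of three is an assumption. LAM, LPS and CMV serve separate research questions (1a, 1b, 1c) and each is sized on its own. If correction applies only within marker panels, LPS tested alone at 0.05 keeps 84% power and nothing is lost. This stands. A reader might infer that the protocol has forfeited its stated LPS capability; the text does not support that, because it never says these three will be corrected together. The definition of families may also sit in an analysis plan that is not at hand.

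Third, a reader might infer that Holm simply keeps LPS at 83%. It does so only if both other exposures differ by their full sized amounts; step 4 of the working shows 72-77% otherwise.

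Fourth, it is tempting to say the same loss recurs in the 13 cytokines and the FACS markers. The protocol gives no effect sizes for the cytokines and sizes only Annexin-V among the FACS markers, so no loss can be computed there. Holm cannot do worse in those panels, but how much better it would do is unknown.

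**Conclusion.** The point holds as a low-severity improvement in efficiency. Wherever a correction is applied, Holm gives the same family-wise control as Bonferroni with power for each comparison that is never lower and usually higher. To call it strictly more powerful would go too far: the gain for LPS is negligible when the other two exposures are null, and there is no gain in the chance of at least one finding.

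In the illustrative three-exposure family, the gain for the 15% LPS difference runs from nothing to about 12 percentage points (72% to 83-84%). These figures rest on two-sided tests, exactly 90 deaths among 600 analysed, the protocol's means and SDs, and normal test statistics with correlations between 0 and 0.5. Holm does not by itself secure 80% power for LPS. That also depends on which comparisons form the family and on the true LAM and CMV effects.

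**What to change.** In Data analysis, replace *Bonferroni correction* with *Holm (Bonferroni-Holm) step-down correction*, and apply it wherever a correction is made, including any marker panels. Report Holm-adjusted p-values with unadjusted confidence intervals, labelled as such.

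The cost is one phrase, with no extra patients or assays. The drawback is that simultaneous confidence intervals matching Holm are less simple than Bonferroni intervals, which is of some weight in an observational study that estimates associations. When making the change, it would help to state which comparisons form a family and to check the 0.05 used for sizing against that choice, since changing the procedure settles neither.

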Appendix 1:

Causes for deterioration on TB treatment among patients presenting to a referral hospital (GF Jooste Hospital) in Cape Town. Causes for deterioration among 352 patients who deteriorated clinically while on TB treatment and required assessment at the referral hospital (GF Jooste Hospital) over a 3-month period in 2007 [20].

Reference: Pepper DJ, Rebe K, Morroni C, Wilkinson RJ, Meintjes G. 2009. Clinical deterioration during antitubercular treatment at a district hospital in South Africa: the importance of drug resistance and AIDS defining illnesses. *PLoS One* 4:e4520.

Appendix 2:**Positive blood culture results from GF Jooste Hospital over a 2-year period**

June 2008 – June 2010. Isolates that were non-pathogenic organisms have been excluded.

Genus or species	Number of isolates
Acinetobacter species	9
Alpha-haemolytic streptococci	16
Beta-haemolytic streptococci	24
Citrobacter species	1
Enterobacter species	14
Enterococcus species	15
E.coli	89
Haemophilus species	9
Klebsiella species	49
Morganella species	4
Neisseria meningitidis	2
Proteus species	12
Pseudomonas species	8
Non-typhi Salmonella species	26
Salmonella typhi	2
Serratia species	1
Shigella species	4
Staphylococcus aureus	57
Streptococcus pneumoniae	60
TOTAL	402

Appendix 3:

[figure not shown]
Factors associated with 2-month mortality in univariate analysis in cohort study of hospitalized HIV-TB patients at Madwaleni Hospital, Eastern Cape, South Africa (preliminary analysis of first participants to complete follow-up, n=79). Consecutive HIV-infected admitted patients started on TB treatment were enrolled in the study.

Variable*	Survivors N=51	Died N=28	p-value for comparison**
Respiratory rate	30 (23-34)	30 (20-35)	0.90
Heart rate	124 (110-140)	117 (103-138)	0.24
Oxygen saturation	96 (95-99)	96.5 (90-98)	0.48
Glucose (mmol/l)	5 (4.1-6.1)	4.5 (2.4-6.5)	0.17
Weight (kg)	49 (43-56)	48 (40-56)	0.68
C-reactive protein (mg/l)	121 (56-209)	207 (117-305)	0.01
Creatinine (µmol/l)	63 (51-104)	150 (77-227)	0.0003
Lactate (mmol/l)	3.2 (2.2-4.1)	5.4 (3.7-6.1)	<0.0001
Haemoglobin (g/dl)	9.0 (6.9-10.2)	7.6 (5.7-9.5)	0.15
CD4 count (cells/µl)	76 (25-190)	31 (14-136)	0.08

* Median and IQR are shown (admission values)

** Wilcoxon rank-sum test

Lactate measurements on admission comparing those who died versus those that survived 2 months:

**Appendix 4:
International Network for the Study of HIV-associated IRIS (INSHI) consensus case definition for paradoxical TB-IRIS that will be used:**

Table I. Case definition for paradoxical TB-IRIS³

There are 3 components to this case definition:

A. Antecedent requirements

Both of the 2 following requirements must be met:

1. Diagnosis of TB: the TB diagnosis was made before starting ART and this should fulfil WHO criteria for diagnosis of smear-positive PTB, smear-negative PTB or extrapulmonary TB
2. Initial response to TB treatment: the patient's condition should have stabilised or improved on appropriate TB treatment before ART initiation – e.g. cessation of night sweats, fevers, cough, weight loss. (Note: this does not apply to patients starting ART within 2 weeks of starting TB treatment since insufficient time may have elapsed for a clinical response to be reported.)

Clinical criteria

The onset of TB-IRIS manifestations should be within 3 months of ART initiation, re-initiation, or regimen change because of treatment failure.

Of the following, at least 1 major criterion or 2 minor clinical criteria are required:

Major criteria

1. New or enlarging lymph nodes, cold abscesses or other focal tissue involvement – e.g. tuberculous arthritis
2. New or worsening radiological features of TB (found by chest X-ray, abdominal USS, CT or MRI)
3. New or worsening central nervous system TB (meningitis or focal neurological deficit – e.g. caused by tuberculoma)
4. New or worsening serositis (pleural effusion, ascites, or pericardial effusion)

Minor criteria

1. New or worsening constitutional symptoms such as fever, night sweats, or weight loss
2. New or worsening respiratory symptoms such as cough, dyspnoea, or stridor
3. New or worsening abdominal pain accompanied by peritonitis, hepatomegaly, splenomegaly, or abdominal adenopathy

C. Alternative explanations for clinical deterioration must be excluded if possible

1. Failure of TB treatment due to TB drug resistance
2. Poor adherence to TB treatment
3. Another opportunistic infection or neoplasm (it is particularly important to exclude an alternative diagnosis in patients with smear-negative PTB and extrapulmonary TB where the initial TB diagnosis has not been microbiologically confirmed)
4. Drug toxicity or reaction

Reference: Meintjes G, Lawn SD, Scano F, Maartens G, French MA, Worodria W, Elliott JH, Murdoch D, Wilkinson RJ, Seyler C, John L, van der Loeff MS, Reiss P, Lynen L, Janoff EN, Gilks C, Colebunders R; International Network for the Study of HIV-associated IRIS. et al. 2008. Tuberculosis-associated immune reconstitution inflammatory syndrome: case definitions for use in resource-limited settings. *Lancet Infectious Diseases* 8:516-523.
